### **Outcome Assessments.**

The primary outcome variable for Aims 1 and 3 is 7-day point prevalence abstinence at Weeks 12 and 24, biochemically-confirmed with urine cotinine (Hughes et al., 2003). Secondary outcomes for Aim 1 include: biochemically-confirmed 7-day point prevalence abstinence at Week 18, smoking rate at Weeks 12, 18, and 24 for non-abstainers, prolonged abstinence to Weeks 12, 18, and 24, continuous abstinence at Weeks 12, 18, and 24, time to 7-day relapse (no grace period), and lapse and recovery events. For Aim 2, since individuals with HIV/AIDS who smoke report a lower QOL (Webb et al., 2007), we will closely monitor QOL, as measured by a commonly-used self-report scale for this population, and administer a checklist of varenicline-related side-effects.

Based on enrollment date, subjects will complete social impact assessments as part of a sub-study in collaboration with the Treatment Research Institute. Two assessments administered at Weeks 3, 7, and 12, include the self-administered, computer based ACASI-SHQ and the staff administered HVTN Social Impact Assessment. An additional client evaluation form is completed by participants at Week 12. Participants who miss administration sessions may complete the assessments at their subsequent study session.

Participants who are unable to quit smoking may be given referrals for smoking cessation treatment following the Week 24 assessment.

**Note:** If a participant is unable to complete a session in-person, assessments and counseling may be completed over the telephone. Participants will receive compensation for their time at the following in-person session.

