### **Other Smoking Measures (secondary)**

As per recommendations (Hughes et al., 2003), secondary smoking outcomes include: prolonged abstinence to Weeks 12 and 24 (relapse is 7 consecutive days of self-reported smoking, after a 2-week grace period), continuous abstinence at Weeks 12 and 24 (no smoking between the quit day and the follow-up; no smoking during weeks 9-12 as measured in previous varenicline trials with the general population of smokers; Gonzales et al., 2006), time to 7-day relapse (no grace period), smoking rate, and lapse (smoking episodes not lasting 7 days) and recovery (return to 24-hour abstinence) events (see [name] et al., 2010b). Abstinence and smoking rate outcome will also be available for Week 18.

**Cessation/Smoking Rate:** Daily smoking (presence and rate) will be assessed at each visit after Intake Session with the well validated timeline followback method (TLFB). These data can be used to assess the timing and rates of lapses (smoking episodes not lasting 7 days), recovery events (return to abstinence), and relapse events, as well as to monitor changes in smoking rates (i.e., # cigarettes/day). These data will also be used to compute and assess secondary measures of smoking cessation (e.g., continuous and prolonged abstinence).

**Carbon Monoxide (CO) Test:** Carbon monoxide will be measured at Intake and all subsequent visits to confirm smoking status.

**NicAlert™ Urine Dipstick (cotinine assessment):** Smoking status will be assessed with NicAlert™ urine dipsticks from Nymox Pharmaceutical Corporation

([http://www.nymox.com/products/nicalert/product\\_insert\\_for\\_urine.html](http://www.nymox.com/products/nicalert/product_insert_for_urine.html)). A midstream urine sample of approximately 25mL will be used to test for the presence of cotinine. Results will appear in one of seven category levels of usage. Level 0 indicates no detectable tobacco use; levels 1-2 indicate presence of cotinine, but as a non-user, and levels 3-6 indicate cotinine consistent with tobacco use. Participants with results in levels 3-6 will be considered smokers. The NicAlert™ urine cotinine assessment will be used to verify smoking status at Weeks 12, 18, and 24.

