**Aim 1: Compare 12-weeks of varenicline treatment and behavioral counseling to 12-weeks of placebo treatment and behavioral counseling for treating nicotine dependence among individuals with HIV/AIDS.** We will analyze quit rates using mixed effects logistic regression. The model will include a term for time-point and, possibly, a *small number of covariates as needed*. The hypothesized effect of treatment arm (placebo vs. varenicline) will be tested by including a dichotomous term for treatment arm; we will also test for an interaction between time-point and treatment. Outcomes of the logistic regression analyses will be characterized by odds ratios (e.g., odds of quitting smoking) and 95% confidence intervals. Although quit-rates at the end of 12 and 24 weeks will represent our primary outcome variables, similar logistic regression analyses will be performed for other measures of quit rates, including prolonged and continuous abstinence. In addition, many participants will fail to become completely abstinent, but may show a reduction in smoking. A secondary analysis will examine the effect of treatment arm on daily cigarette counts using mixed effects negative-binomial regression. Likewise, time to (recurrent) event models will be fitted using Cox regression, stratified by event sequence, as in [name] et al. (2010b), to assess lapse and recovery events over 24 weeks.

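### On its natural reading, the Aim 1 mixed-effects logistic model does not suit prolonged and continuous abstinence: the arm odds ratio and its interval would depend on software settings

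*Combined protocol and SAP*

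**What the plan says.** Data Analysis, Aim 1, opens with "We will analyze quit rates using mixed effects logistic regression". It goes on: "The model will include a term for time-point", a dichotomous arm term is added, and "we will also test for an interaction between time-point and treatment". On reporting it says "Outcomes of the logistic regression analyses will be characterized by odds ratios", with 95% confidence intervals. After naming the Week 12 and Week 24 quit rates as primary, it adds that "similar logistic regression analyses will be performed for other measures of quit rates, including prolonged and continuous abstinence".

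Outcome Assessments schedules "prolonged abstinence to Weeks 12, 18, and 24, continuous abstinence at Weeks 12, 18, and 24". Other Smoking Measures (secondary) defines continuous abstinence as "no smoking between the quit day and the follow-up", and also mentions a Weeks 9-12 window. In the same section, prolonged abstinence fails at a seven-day relapse after a two-week grace period.

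The random effect is not named. The software is left open among Stata, SAS and R, and no estimation method or quadrature rule is given. The Missing Data paragraph counts participants without smoking outcome data as smokers.

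**The concern.** The repeated-measures model suits seven-day point prevalence, because a participant can be smoking at Week 12 and abstinent at Week 24, or the reverse. Prolonged and continuous abstinence are different. Each counts from the quit day or the end of the grace period, and no route back after failure is given, so a Week 24 success must also be a Week 12 success.

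A random-intercept logistic model with finite parameters always gives the no-to-yes pattern a positive probability. If the data cannot contain that pattern, the fit improves as the parameters move towards infinity. The quantity to be reported, a subject-specific odds ratio with its interval, then reflects where the program stops. Two competent analysts following the plan on the same data could publish very different numbers.

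**Working it through.** The plan states no figure for these models, so there is none to reproduce.

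**Inputs.** The sample is 310 (Power, Aim 1), and half receive varenicline (Risk/Benefit Assessment), so 155 per arm. No rates are given for the cumulative outcomes. As an assumption, the planning rates for point prevalence stand in: Week 12, 21.2% and 50.3%; Week 24, 14.5% and 33.5%. Multiplied by 155 and rounded, they give 33 and 78 successes at Week 12, and 22 and 52 at Week 24. With nesting, the pairs (Week 12, Week 24) are:

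| Arm | yes, yes | yes, no | no, yes | no, no |
|---|---|---|---|---|
| Placebo | 22 | 33 − 22 = 11 | 0 | 122 |
| Varenicline | 52 | 78 − 52 = 26 | 0 | 77 |

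**Mechanism.** Take logit P(yes) = a + b·arm + c·time + u, with u normal with standard deviation SD. For any value of u, P(yes, no)/P(no, yes) = exp(−c), so the ratio also holds after averaging over u. With finite c and SD, P(no, yes) is above zero, but its observed count is zero. At a fixed SD, c is finite: −1.06, −2.14, −3.90 and −7.46 at SD 2, 5, 10 and 20. The divergence runs through the SD, and the coefficients scale up with it.

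**Profile over the SD** (main-effects model, near-exact numerical integration):

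| SD | log-likelihood | arm odds ratio | log odds ratio / SD |
|---|---|---|---|
| 0 | −350.03 | 3.4 | – |
| 2 | −292.54 | 7.6 | 1.02 |
| 5 | −266.04 | 58 | 0.81 |
| 10 | −260.16 | 2,125 | 0.77 |
| 20 | −259.31 | 3.5 million | 0.75 |

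The log-likelihood levels off at −259.288 from SD 50 upwards, while the odds ratio goes on growing. With the interaction term, it climbs from −292.19 at SD 2 to −258.39 at SD 20, towards the saturated multinomial value of −258.343, which no finite parameters reach.

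**What software returns.** R's lme4, on this one dataset, gives an arm odds ratio of 4.26 (Laplace), 7.0 × 10⁸ (5 quadrature points), 61 (7), 1.8 × 10⁹ (15) and 1.1 × 10⁸ (25).

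**Test of arm.** Twice the log-likelihood difference with and without arm is 34.8, 29.4, 27.6 and 27.2 at SD 2, 5, 10 and 20. It settles, although the odds ratio does not.

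**A few no-to-yes patterns.** Moving participants from (no, no) to (no, yes) gives a finite maximum. On a coarse SD grid the arm odds ratio is about 1,700 with one such participant, 107 with five, 53 with eight and 13 with twenty. A finer search gives 114 with five and 17 with twenty.

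**Models without a subject random intercept, same counts.**
- Week 12: odds ratio (78 × 122)/(33 × 77) = 3.74. The standard error of the log is √(1/78 + 1/33 + 1/77 + 1/122) = 0.254, so the 95% CI is 2.28 to 6.16. Risk difference 45/155 = 29.0 points.
- Week 24: odds ratio (52 × 133)/(22 × 103) = 3.05, standard error 0.286, 95% CI 1.74 to 5.35. Risk difference 30/155 = 19.4 points.
- Marginal (GEE) model over both weeks: 3.58 (2.19 to 5.84).

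**The case against.** The strongest reply is that the plan does not clearly prescribe this model. The sentence on prolonged and continuous abstinence speaks of *similar* logistic analyses without repeating the mixed-effects label, and the outcomes are worded week by week. Ordinary logistic regression at each visit is a possible reading, and it works. This stands as a limit on certainty. But the only logistic model described in that paragraph is the mixed-effects one, and nothing says that the random effect or the pooling over time is dropped.

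Second, missing-equals-smoking coding applied visit by visit could produce no-to-yes patterns, so a finite estimate may exist. That is correct, but such coding conflicts with the cumulative definitions and the estimates remain far too large.

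Third, the Weeks 9-12 definition used alone is a single time-point with nothing to pool. That is also correct. Paired with abstinence from quit day to Week 24, however, it is still nested.

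Fourth, an odds ratio in the thousands would be noticed. Some would, but the Laplace result of 4.26 looks unremarkable, although the same data give 61 with seven quadrature points.

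Finally, the planned Cox models do not fill the gap: Aim 1 assigns them to lapse and recovery events, not to these binary outcomes.

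**Conclusion.** The concern holds for the natural reading of Aim 1: a subject random intercept with Weeks 12 and 24 (or 12, 18 and 24) pooled. On that reading the arm odds ratio and its 95% interval for prolonged and continuous abstinence are not usable. In the illustration, marginal odds ratios of 3 to 4 turn into values from 4.26 to above 10⁹, depending on the quadrature setting alone. The counts are assumed, but the divergence comes from the empty no-to-yes cell and not from the rates. Only two time-points were computed; adding Week 18 keeps the nesting.

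A reader might infer more than this, and the documents do not support it:
- Failure is not certain, because the sentence allows a per-visit reading.
- The results would not be wholly detached from the data, because an accurately integrated likelihood-ratio test of arm remains stable.
- The protocol does not rank these two as its main secondary outcomes.
- The primary seven-day point-prevalence outcome can move in both directions and is not affected.

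**What to change.** In Data Analysis, Aim 1, replace the sentence on other measures of quit rates with one stating that prolonged and continuous abstinence will each be analysed by ordinary logistic regression at each time-point, reporting the odds ratio and risk difference with 95% confidence intervals, or alternatively by one time-to-first-failure model. Name the choice in advance, and state that the mixed-effects model is kept for point prevalence only. It would help to add that a missing visit is coded in line with the cumulative definition, so that a failure at one week carries forward to later weeks.

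The cost is a sentence or two of text. No new data, visits or participants are needed, and the analysis is simpler than the one it replaces.

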### 3. Key Inclusion Criteria

Eligible subjects will be males and females:

1. 18 years of age or older who self-report smoking at least 1 cigarette (menthol and non-menthol) per day, on average.
2. Diagnosed with HIV infection and exhibiting viral load of  $\leq 1000$  copies/mL within the last 6 months.
3. Exhibiting CD4+ count of  $\geq 200$  cells/mm^3 within the last 6 months.
  1. If the participant has not had a CD4+ count test completed in the last 6 months, an older result ( $\geq 200$  cells/mm^3) may be used if evidence is provided that all subsequent viral loads results are  $\leq 1000$  copies/mL.
4. Able to use varenicline safely, based on a medical evaluation including medical history and psychiatric evaluation.
5. Residing in the geographic area for at least 7 months.
6. Women of childbearing potential (based on medical history) must consent to use a medically accepted method of birth control (e.g., condoms and spermicide, oral contraceptive, Depo-Provera injection, contraceptive patch, tubal ligation) or abstain from sexual intercourse during the time they are taking study medication and for at least one month after the medication period ends.
7. If current or past diagnosis of bipolar disorder (I, II, or NOS), eligible if:
  - a. No psychotic features
  - b. MADRS: total score  $\leq 8$  (past 4 weeks), suicidal item score  $\leq 1$  (past 4 weeks)
  - c. Y-MRS: total score  $\leq 8$  (past 4 weeks), irritability, speech content, disruptive, or aggressive behavior items score  $\leq 3$  (past 4 weeks)
  - d. No psychiatric hospitalization or Emergency Room visits for psychiatric issues in the past 6 months

- e. No aggressive or violent acts or behavior in the past 6 months
- 8. Able to communicate fluently in English.
- 9. Capable of giving written informed consent, which includes compliance with the requirements and restrictions listed in the combined consent/HIPAA form.

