### **Intake Session (Week -1): Consent, Eligibility Determination, Baseline Measures.**

Subjects who pass the pre-screening will be invited to attend a 2.5-hour Intake Session where the following activities will occur:

1. Subjects will hear a study description where all study procedures, risks, and information about the study medication will be reviewed. Subject questions will be answered. Following this presentation, the combined informed consent and HIPAA form will be completed.
2. A urine pregnancy test (all female subjects) will be administered.
3. A breath alcohol concentration assessment (BrAC) to control for alcohol consumption. The handheld device uses a disposable mouthpiece, reports the concentration of alcohol in breath and takes about 2 minutes.
4. A carbon monoxide (CO) breath assessment to control for prior tobacco exposure. The handheld device uses a disposable mouthpiece, reports CO in parts per million (ppm), and takes about 3 minutes.
5. Mental status examinations (Mini International Neuropsychiatric Interview, HADS, C-SSRS, and MADRS, YMRS, Bipolar Disorder Additional Screener, if necessary) with a trained research staff member.
6. Complete routine medical history, including blood pressure assessment.
7. A concomitant medication review.
8. Complete baseline paper and pencil measures to assess 1) background variables that may serve as covariates and will allow for the assessment of the study's external validity (e.g., smoking history, demographics), 2) mediators (e.g., affect, cognition), 3) moderators (e.g., disease-related information, and 4) baseline smoking behavior.
9. Provide one 10ml blood sample (2 teaspoons) to assess nicotine metabolite ratio (cotinine and 3-hydroxycotinine).
10. Provide one 10ml blood sample (2 teaspoons) for DNA collection and genotyping.

Initially eligible participants who have not had kidney function tests within the last 6 months (as ascertained by medical record review or provision of results from the participant's health care provider) will provide one 10ml blood sample (2 teaspoons) to complete these tests following the Intake Session. Test results that are outside of normal ranges will be reviewed for final eligibility by the Study Physician prior to enrollment.

If eligible at this point, subjects will be scheduled for the first treatment session (Week 0).

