### **Data Analysis**

[name] will oversee analyses which will be conducted using Stata, SAS, or R-Language software. Preliminary analyses will assess sample characteristics by treatment with chi-square or logistic regression (e.g., gender, dependence, depression). These variables will also be examined for their relationship to completion of outcome assessments. Variables related to treatment arm or completion of follow-ups will be included as covariates in analyses of study aims. Compliance measures will be evaluated across treatment arms, and controlled for in primary analyses. We will examine the correlation between self-report and pill count data and week 3 and 12 varenicline levels. Although we will use intent-to-treat as the primary method for

[figure not shown]
evaluating study aims, we will conduct a completers only analysis of study aims and examine study aims with participants lost to follow-up due to death excluded as done previously ([name] et al., 2003).

**Missing Data:** We will examine if the rate of missing data, primarily our smoking cessation outcome data, is related to a range of potential variables, including treatment arm allocation and HIV/AIDS-related, demographic, and smoking-related variables. Standard statistical methods will be used to identify possible correlates of missing data such as chi-square and regression. Variables found to be associated with the rate of missing data ( $p < .05$ ) will be included as covariates in the analyses of aims. In the event of items missing at random on measures, items will be imputed prior to calculating final scores using conditional means, estimated with an iterated version of Buck's method (Gleason & Staelin, 1975). Dropout and missed sessions present a more serious issue. The best way to deal with this is to avoid the problem in the first place by keeping subjects connected to the trial and motivated to complete measures. In our clinical trials, compliance and retention rates were >80% thanks to our close monitoring of participants and use of incentives to offset travel costs ([name] et al., 2008). Primary analyses will assume that all subjects for whom smoking outcome data are unavailable are smokers (intent-to-treat). This assumption, which is conventional in smoking cessation research, can attenuate the differences between study groups in quit rates. Thus, we will also conduct a "completers-only" analysis.

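### The secondary analysis of daily cigarette counts does not commit to adjusting for each participant's recorded pre-treatment smoking rate, which gives up some precision

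*Combined protocol and SAP*

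**What the plan says.** The count analysis is specified in one sentence of Data Analysis, Aim 1: "A secondary analysis will examine the effect of treatment arm on daily cigarette counts using mixed effects negative-binomial regression". No baseline rate, offset or change score is named. The sentence before it gives the purpose: some participants may cut down without quitting.

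Covariates are mentioned in three other places.

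- For the quit-rate logistic model in the same paragraph: "The model will include a term for time-point and, possibly, a" small set of unnamed covariates as needed.
- For all aims, at the start of Data Analysis: "Variables related to treatment arm or completion of follow-ups will be included as covariates in analyses of study aims". The Missing Data paragraph adds that variables associated with missingness at p < .05 "will be included as covariates in the analyses of aims".
- The Intake Session list says that background variables, with smoking history as an example, may serve as covariates. It separately lists "4) baseline smoking behavior" among the measures taken.

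Demographic and Smoking History includes current rate. Under Other Smoking Measures, "Daily smoking (presence and rate) will be assessed at each visit after Intake Session", and Table 2 marks the timeline follow-back from Week 0. Behavioral Counseling says that medication starts at or just after that session, so the Week 0 record describes smoking before dosing. Outcome Assessments defines the smoking-rate outcome at Weeks 12, 18 and 24 for non-abstainers.

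**The concern.** When an outcome is also measured before treatment, its baseline value is usually the strongest available predictor, and adjusting for it narrows the interval for the arm effect. Here a baseline is collected and the model does not commit to using it. The mixed-effects structure does not make up for this. A participant random effect accounts for correlation among one person's repeated counts, but arm varies between people, so its standard error still carries the between-person variance.

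Entry admits anyone who can "self-report smoking at least 1 cigarette (menthol and non-menthol) per day, on average", with no upper limit. (Target Population gives 5 per day, also with no upper limit.) A wide spread of consumption is therefore possible.

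At stake is the precision of the analysis meant to detect reduced smoking. There is also a smaller point of pre-specification: under the conditional rules, whether baseline rate enters depends on what the data happen to show about imbalance and dropout.

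**Working it through.** **1. Is there a stated figure to reproduce?** No. The Power section gives no effect size, variance, correlation or power for cigarette counts. As a check on sample size and alpha only, the quality-of-life figure reproduces. With 155 per arm, a difference of 7.8 and SD 24.5, the standardised statistic is 7.8 / (24.5 × √(2/155)) = 2.80. Power is Φ(2.80 − 1.96) ≈ 0.80, as stated.

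**2. Does any covariate rule commit to the baseline rate?**

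| Text | Applies to | Brings in baseline rate? |
|---|---|---|
| Aim 1, covariates as needed | Quit-rate logistic model | Not named |
| Data Analysis, general rule | All aims | Only if related to arm or completion |
| Missing Data | All aims | Only if associated with missingness |
| Intake Session list | Background variables | Permitted, not required |

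None adds baseline rate because it predicts the outcome.

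**3. Linear approximation.** Let ρ be the correlation between baseline and follow-up. The documents give no value, so it is assumed. Adjustment multiplies the between-person variance by 1 − ρ². If the unadjusted comparison has 80% power (two-sided 0.05), adjusted power is Φ((1.96 + 0.84)/√(1 − ρ²) − 1.96). The equivalent unadjusted sample is 310/(1 − ρ²).

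| Assumed ρ | 1 − ρ² | Adjusted power | Equivalent unadjusted N |
|---|---|---|---|
| 0.2 | 0.96 | 81.6% | 323 |
| 0.3 | 0.91 | 83.6% | 341 |
| 0.5 | 0.75 | 89.9% | 413 |
| 0.7 | 0.51 | 97.5% | 608 |

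**4. Simulated counts, everyone still smoking.** Assumptions: 155 per arm, rate ratio 0.80, log-SD of baseline 0.6, overdispersed counts averaged over three visits, log-link regression with robust standard errors, 1,000 replicates. This approximates the planned mixed model and is not identical to it. Power without and with log baseline was:

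- 69.8% and 71.4% with a weak baseline link (slope 0.3);
- 58.2% and 68.7% at slope 0.6;
- 55.3% and 76.7% at slope 0.9;
- 70.7% and 96.4% at slope 0.9 with little residual spread.

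With a true rate ratio of 1.0, rejection ran from 4.6% to 6.2% across both analyses, so the term did not materially change the error rate.

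**5. Simulated counts, quitters included as zeros.** Assumptions: 155 per arm, log-SD 0.7, seven days of counts, log-link regression with robust standard errors, 600 replicates, Monte Carlo error about 2 points. The first three rows use the Week 24 quit rates in the Power section (14.5% placebo, 33.5% varenicline), unrelated to baseline rate, with no arm effect among continuing smokers.

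| Scenario | Unadjusted | Adjusted | Gain (points) |
|---|---|---|---|
| 14.5%/33.5% quit, ρ 0.3 | 55.2% | 56.5% | 1.3 |
| 14.5%/33.5% quit, ρ 0.5 | 54.8% | 59.8% | 5.0 |
| 14.5%/33.5% quit, ρ 0.7 | 54.5% | 65.7% | 11.2 |
| 25% quit in both arms, rate ratio 0.80, ρ 0.5 | 46.3% | 51.8% | 5.5 |

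In the same set-up with no quitters, rate ratio 0.80 and ρ 0.5, power went from 69.7% to 79.2%, a gain of 9.5 points. Zeros unrelated to baseline roughly halve the gain at ρ 0.5.

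**The case against.** The strongest case against is that this is a preference about efficiency in a secondary analysis for which the plan makes no power claim. Randomisation protects an all-randomised comparison without the term. If baseline rate turned out to be related to arm, the general rule would add it, so chance imbalance is already partly handled. The gain is unknown, and once quitters are counted it may be only a point or two. All of this stands. What remains is that the plan does not commit to a useful covariate that it already collects.

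Three stronger readings are tempting, and the documents support none of them.

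- *That between-person differences swamp the arm effect.* This needs a variance, a correlation and an effect size for cigarette counts, and none is given. The lack of an upper entry limit permits a wide spread but does not show one.
- *That Week 0 counts dilute the estimate.* This would follow if pre-dose days entered as outcomes under a single arm term. The model sentence does not say which days it uses, but Outcome Assessments lists Weeks 12, 18 and 24, which points away from that reading.
- *That the model should move to all randomised participants and all days after the quit date.* That would change the population and time window in Outcome Assessments. A comparison confined to non-abstainers does contrast subsets formed after randomisation, but that is a separate and larger question, and a baseline term does not answer it.

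**Conclusion.** The point holds as a minor improvement. The plan permits adjustment for pre-treatment smoking rate in the count model but does not pre-specify it, and the participant random effect is no substitute.

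The benefit is precision. Its size depends wholly on an assumed correlation. The linear gains of about 4, 10 and 17.5 points at ρ 0.3, 0.5 and 0.7, from a base of 80%, are upper-end illustrations. With quitters' zeros included, about 1 to 11 points is more realistic over the same range. The primary abstinence comparison does not depend on this. The statement that the unadjusted comparison is unbiased applies to all randomised participants; it does not extend to an analysis restricted to non-abstainers.

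**What to change.** In Data Analysis, Aim 1, add to the count-model sentence that log baseline cigarettes per day will be a fixed covariate in the mixed effects negative-binomial regression. State that counts from before the first dose serve only as baseline and not as outcome data. Name which record supplies the baseline (the Intake rate or the Week 0 timeline follow-back) and use the other if it is missing. The entry criterion of at least one cigarette per day keeps the logarithm of the Intake rate defined. Leave the analysis population and time points as Outcome Assessments defines them.

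The cost is a sentence or two of wording, settled before unblinding. No new data are needed, and the model gains one parameter.
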